9.1.3. HPV vaccine coverage in UK and in CPRD GOLD

The submitted study is in the UK, which is a country with a high Cervarix vaccine coverage. The recommended schedule in the UK for HPV vaccination of 12-13 year old girls involves three doses of Cervarix given over at least a 6-month period [DH, 2008; HPA, 2010].

In the UK public HPV immunization program (12-13 year olds), HPV vaccination coverage in the UK for 2010/11 was 89.0%, 87.6% and 83.8% for the first, second and third dose respectively [Health Protection Agency, 2012].

Vaccination records in the CPRD GOLD cover only part of the Cervarix-vaccinated population in the UK. For instance, 70.7% of the 01-SEP-1996 – 31-AUG-1997 birth cohort were reported as HPV vaccinated in CPRD GOLD versus 85.9% reported by the UK Health Protection Agency. Corresponding numbers for the 01-SEP-1994 – 31-AUG-1995 birth cohort are 70.6% versus. 81.9% (Table 2).

Table 2 HPV vaccination coverage in CPRD GOLD versus HPA-DH UK data

	CPRD† UK‡			UK‡
Birth cohort	N vaccinated	N total	%	%
01 SEP 1996 and 31 AUG 1997	16028	22685	70.7%	85.9%
01 SEP 1994 and 31 AUG 1995	16343	23143	70.6%	81.9%

† Data extracted from CPRD GOLD version ffqprd_smart_2012Q3

‡ From Health Protection Agency Department of Health [Health Protection Agency, 2012]

A first exploration of the CPRD GOLD database identified 148,731 subjects vaccinated with Cervarix between 2007 and 2010. The number of vaccinated women in the relevant age-range included in the CPRD GOLD is provided in Table 3. The number of HPV-vaccinated females in the CPRD GOLD appears to be sufficient for studying adverse events which have a low incidence after vaccination with Cervarix.

Table 3 Number of HPV-vaccinated females in the relevant age range included in the CPRD GOLD

Age range [years]	Number of subjects
[9-10]	16
[11-15]	82326
[16-20]	65080
[21-25]	866

Created by GSK Biologicals', 2012

Date extracted from CPRD GOLD version ffgprd_smart_2012Q3

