9.2.1. The UK HPV National Immunization Programme

The submitted study is in the UK, which is a country with a high Cervarix vaccine coverage. The recommended schedule in the UK for routine HPV vaccination of all girls at 12 to 13 years of age is [DH, 2008; HPA, 2010]:

- Vaccination at this age starts with a first dose of 0.5ml of Cervarix HPV vaccine
- The second dose of 0.5ml follows one to two months after the first dose
- A third dose of 0.5ml follows at least six months after the first dose

The UK has had sufficient Cervarix vaccination coverage to, in theory, enable data acquisition. A public immunisation programme targeting girls between 12-13 years of age including a catch-up programme for young women up to 18 years was undertaken during the academic year 2008/09. A phased catch-up programme for females born 1 September 1991 to 31 August 1995 during the 2008/09 academic year was completed by the end of the 2009/10 academic year. The programme was delivered largely through secondary schools [Crawford, 2009; Sheridan, 2009; Sheridan, 2010]. In the UK public HPV immunization program (12-13 year olds), HPV vaccination coverage in the UK for 2010/11 was 89.0%, 87.6% and 83.8% for the first, second and third dose respectively [Health Protection Agency, 2012]. The recommended age range for the UK programme matches the age range required by the FDA (9-25 years of age) for the post-licensure safety study.

The study population will be composed of female and male subjects, 9 to 25 years of age, registered in the CPRD GOLD.

The exposed cohort will be composed of female subjects vaccinated with at least one dose of Cervarix, with or without other recommended vaccines.

The unexposed historical female cohort will consist of frequency age-matched and practice region-matched female subjects from the period before the introduction of Cervarix. The unexposed concurrent male cohort will consist of frequency age-matched and practice region-matched by one-year classes (15, 16, 17, etc.) male subjects from the

period after the introduction of Cervarix. The unexposed historical male cohort will consist of frequency age-matched and practice region-matched male subjects from the period before the introduction of Cervarix.

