9.2.2. Cohort identification and creation

The exposed eligible cohort have been identified based on the stepwise approach defined in Annex 5. Among eligible exposed subjects, 65,000 subjects will be randomly selected using the RANUNI function of SAS. The RANUNI function returns a number that is generated from the uniform distribution on the interval (0, 1). The corresponding subject number will be computed as *random_subj_number=ranuni(seed)*. The subjects will be ordered according the *random_subj_number* and the first 65,000 subjects will be included in the exposed cohort.

The unexposed eligible cohorts have been identified based on the stepwise approach define in Annex 5.

All the unexposed subjects who matched exposed subject for age (birth cohort) and region (frequency matching) will be identified. This represents 234 combinations of birth cohort-region (18 birth cohorts and 13 regions in CPRD GOLD). In each combination, the subjects will be randomly selected based on the distribution in the exposed cohort.

A reference date is randomly attributed to all potential unexposed subjects. For the concurrent male cohort, the reference date is a random date between 01-SEP-2008 and 31-AUG-2010. For the historical cohorts, the reference date is a random date between 01-SEP-2005 and 31-AUG-2007 (reference dates for exposed cohort – 3 years).

The random reference dates in each 'birth cohort-region" combination will be attributed randomly using the RANUNI function of SAS.

The age at reference date will be calculated for the unexposed cohort. After applying the exclusion criteria, the eligible subjects (65,000 subjects in each cohort) will be randomly selected in each of the combinations 'birth cohort-region' taking into account the distribution in the exposed cohort. The random selection will also use the RANUNI function of SAS.

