9.2.4.1. Inclusion criteria for the exposed female cohort

Exposed females must satisfy ALL the following criteria at study entry:

- Female aged from 9 to 25 years at the reference date (01 September 2008 through 31 August 2010)
- Recorded in the CPRD GOLD for at least 12 months before the reference date
- The first dose of Cervarix received between 01 September 2008 through 31 August 2010, Full date (day/month/year) of Cervarix vaccination(s) available
- Subject defined as acceptable in CPRD GOLD

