9.2.4.2. Inclusion criteria for the unexposed historical female cohort

Unexposed females must satisfy ALL the following criteria at study entry:

- Female aged 9 to 25 years at the reference date (01 September 2005 through 31 August 2007)
- Recorded in the CPRD GOLD for at least 12 months before the reference date
- Subject defined as acceptable in CPRD GOLD

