9.2.5. Exclusion criteria

9.2.5.1. Exclusion criteria for all cohorts

- Subjects with a diagnostic code of any auto-immune disease during the year prior to the reference date.
- Subjects who received at least one dose of unspecified HPV vaccine or Gardasil at any time before the reference date.
- Subjects who have been included in the other cohort.

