9.2.5.2. Exclusion criteria for the non-exposed cohorts

• Subjects who received any dose of Cervarix at any time before the reference date.

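### The bar on subjects included in the other cohort, if the exposed are drawn first, makes 2005-07 control eligibility depend on the outcome through a later event and can pull the primary rate ratio down

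*Protocol*

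**What the plan says.** Section 9.2.5.1 lists, for all cohorts, the exclusion of "Subjects who have been included in the other cohort". It gives no order of precedence. The same list excludes "Subjects with a diagnostic code of any auto-immune disease during the year prior to the reference date".

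Section 9.2.2 describes the order of work: "Among eligible exposed subjects, 65,000 subjects will be randomly selected using the RANUNI function of SAS". The unexposed are then drawn, after the exclusion criteria have been applied, to follow the exposed distribution. That section forms strata by birth cohort and region, whereas section 9.1.2 matches on one-year age classes at the reference date.

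The two female cohorts are separate in time. Exposed entry requires "The first dose of Cervarix received between 01 September 2008 through 31 August 2010" (section 9.2.4.1). Historical reference dates run from 1 September 2005 to 31 August 2007 (section 9.2.4.2), with 12 months of follow-up (section 9.7.5.1). The non-exposed cohorts further exclude only "Subjects who received any dose of Cervarix at any time before the reference date" (section 9.2.5.2), so later vaccination by itself does not disqualify a historical control.

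**The concern.** A control group should be chosen on what is known at its own reference date. Here, on the order described in section 9.2.2, a girl's place in the 2005-07 pool depends on whether she is sampled as exposed one to five years later. That later selection depends on her recent autoimmune history.

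Take two girls in the pool, one with onset in the historical year and one without. Both are vaccinated in 2008-10. If the first has an autoimmune code in the year before her dose, she cannot be exposed and remains a possible historical case. The second can be sampled as exposed and then leaves the pool. Non-cases are removed more often than cases.

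The comparison affected is the primary one, exposed against historical females (section 9.7.5.1). A historical rate that is too high makes a vaccine risk harder to see, which is the unfavourable direction in a safety study. The limitations in section 9.9 do not mention this selection.

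**Working it through.** **The plan's own figure.** Section 9.5.1 gives detectable relative risks of 18.7, 3.7, 2.0 and 1.6 at background rates of 1, 10, 50 and 100 per 100,000 person-years (50,000 per cohort, 80% power, alpha 0.05). A two-sided pooled comparison of two proportions gives 18.49, 3.72, 1.96 and 1.64, so the figures reproduce. At exactly 1.6 and 100 per 100,000, power is 75%.

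**Do the cohorts share people?** The programme included "A phased catch-up programme for females born 1 September 1991 to 31 August 1995" (section 9.2.1). Those births were about 10 to 16 years old at a 2005-07 reference date, so they were eligible for the historical cohort.

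**Share removed.** A first look at the database "identified 148,731 subjects vaccinated with Cervarix between 2007 and 2010" (section 9.1.3).
- Sampled share of vaccinees: 65,000 / 148,731 = 0.437.
- Recorded coverage, Table 2: (16,028 + 16,343) / (22,685 + 23,143) = 0.706.
- Share of an overlapping birth cohort removed: 0.706 x 0.437 = 0.309, if everyone is registered at both dates.

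**Model** (rare disease). Let v be the share of the overlapping pool removed. Let s be the probability that a historical case carries an autoimmune code in the year before the later dose. Let w be the share of the historical cohort lying in overlapping births, and r the share of persons registered at both dates, so v = 0.309 x r. Non-cases are retained with probability 1 - v and cases with probability 1 - v(1 - s). Hence, in overlapping strata,

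F = (1 - v(1 - s)) / (1 - v) = 1 + s v / (1 - v),

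and over the whole cohort F = 1 + w s v / (1 - v). The observed rate ratio is the true one divided by F.

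**Assumed inputs.** The protocol gives none of s, r or w.
- s: 0, 0.5 and 1.
- w: 1 under birth-cohort matching. Under age matching I use 0.55, close to the 11-15 share in Table 3 (82,326 / 148,288 = 0.555).
- r: 1, 0.7 and 0.455. The last reads the section 9.5.1 allowance as an annual loss over three years: (50,000 / 65,000)^3 = 0.455.

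| Matching | r | v | v/(1-v) | F, s = 0 | F, s = 0.5 | F, s = 1 |
|---|---|---|---|---|---|---|
| Birth cohort (w = 1) | 1 | 0.309 | 0.447 | 1.00 | 1.22 | 1.45 |
| Birth cohort (w = 1) | 0.7 | 0.216 | 0.276 | 1.00 | 1.14 | 1.28 |
| Age (w = 0.55) | 1 | 0.309 | 0.447 | 1.00 | 1.12 | 1.25 |
| Age (w = 0.55) | 0.7 | 0.216 | 0.276 | 1.00 | 1.08 | 1.15 |
| Age (w = 0.55) | 0.455 | 0.141 | 0.164 | 1.00 | 1.04 | 1.09 |

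A simulation with v of about 0.31 gave 1.45, 1.22 and 1.00 for s = 1, 0.5 and 0, in agreement with the formula.

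**Consequence for a true rate ratio of 1.6** at 100 per 100,000, 50,000 per cohort:
- Birth-cohort matching, r = 1: seen as 1.6 / 1.447 = 1.11 (s = 1) or 1.6 / 1.224 = 1.31 (s = 0.5). Power falls from 75% to 9% or 36%.
- Age matching, r = 1: seen as 1.28 or 1.42, with power 31% or 53%.
- Age matching, r = 0.7: seen as 1.39 or 1.49, with power 48% or 62%.

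**The case against.** The strongest reply is that the protocol never states that the exposed take precedence. The bullet applies to all cohorts, and section 9.2.2 refers to the stepwise approach in Annex 5, a stand-alone document not shown here. If the historical cohort took precedence, this bias of the historical rate would not arise. That stands as a qualification. The order described in section 9.2.2 still points to exposed first, and leaving the precedence open is itself a gap.

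Four stronger readings are tempting, and the documents do not support them.
- That all future vaccinees leave the pool. Only those sampled do, about 44% of 148,731.
- That exposed girls must never have had an autoimmune code. The look-back is one year, so a historical case with no code in that year can still be sampled as exposed. Section 9.1.2 itself names Guillain-Barré syndrome as acute, and acute disease may leave little later coding.
- That the rate ratio is certainly too low on balance. Section 9.1.2 says unvaccinated women may differ in health care behaviour and in the chance of detection. Removing recorded vaccinees enriches the pool in such women, which could act either way.
- That a particular factor is established. The 1.45 needs literal birth-cohort matching, no attrition and full re-coding. Section 9.4.1 reports a median follow-up of 5.0 years, so attrition matters.

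Two safeguards exist but do not repair the primary comparison. The self-controlled case series uses no historical cohort, but it is a separate analysis. The male cohorts might carry a similar distortion that partly offsets this one, but their order of selection is not stated, and the adjustment is made only after a significant male difference (section 9.7.5.1).

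**Conclusion.** The point holds in this form. On the order described in section 9.2.2, the cross-cohort bar makes historical eligibility depend on the outcome through a later event. Within this mechanism the historical rate can only rise and the primary rate ratio can only fall. The net direction, once health care behaviour is included, is not settled.

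The size is illustrative. It is nil without codes in the look-back year. Under age matching with 50-100% re-coding the factor is about 1.04-1.25, so the rate ratio is multiplied by about 0.96-0.80. The upper end is 1.45 (rate ratio times 0.69). These figures rest on assumed re-coding, retention and overlap, on exposed-first sampling, and on cases and non-cases being otherwise equally likely to be vaccinated and registered. Composite [2] contains type 1 diabetes, thyroid and inflammatory bowel disease, for which repeat coding is a reasonable assumption, though not one the protocol documents.

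**What to change.** Define eligibility for the historical cohorts only by information up to the historical reference date. In section 9.2.5.1, drop the cross-cohort exclusion between historical and recent cohorts, for females and males alike. Historical follow-up ends by 31 August 2008 and exposed follow-up starts no earlier than 1 September 2008, so one person can contribute separate person-time to both. Count only a person's first-ever autoimmune disease, in the same way in all four cohorts, and use a variance that allows for repeated persons.

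The cost is wording and sampling code, settled before the cohorts are drawn. The small downside is that some subjects appear twice.

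If distinct persons are required, patient identifiers can be split at random between a historical and a recent frame before vaccination or diagnosis records are consulted. Half of 148,731 is about 74,400, but that is an exploratory count not shown to be net of all entry criteria. This route is open only if the eligible number after those criteria still supports 65,000. If the bar is kept at all, state the precedence and add a sensitivity analysis without it.

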9.2.5.2. Exclusion criteria for the non-exposed cohorts

• Subjects who received any dose of Cervarix at any time before the reference date.

9.3. Variables

9.3.1. Primary endpoint

• Occurrence of new onset of confirmed⁴ autoimmune disease during the period of one year following administration of the first dose of Cervarix (risk period) among an exposed cohort and during an equivalent time period in the unexposed cohorts for the following two co-primary composite endpoints:

[1] Neuroinflammatory/ophthalmic autoimmune diseases:

- Multiple Sclerosis
- Transverse myelitis
- Optic neuritis
- Guillain-Barré syndrome, including Miller Fisher syndrome and other variants
- Other demyelinating diseases:
 - Acute disseminated encephalomyelitis, including site specific variants: e.g. non-infectious encephalitis, encephalomyelitis, myelitis, myeloradiculomyelitis
 - AI peripheral neuropathies and plexopathies (including chronic inflammatory demyelinating polyneuropathy, multifocal motor neuropathy and polyneuropathies associated with monoclonalgammopathy).
- Auto-immune uveitis

[2] Other autoimmune diseases:

- Systemic lupus erythematous
 - Autoimmune (AI) disease with rheumatologic conditions:
 Rheumatoid arthritis (RA)

⁴ Auto-immune disease diagnosis ascertainment by an expert physician panel (Section 9.4.2).

- Juvenile rheumatoid arthritis (JRA)
- Still's disease
- Psoriatic arthritis
- Ankylosing Spondylitis
- AI haematological conditions:
 - Idiopathic thrombocytopenic purpura (ITP)
 - AI haemolytic anaemia
- AI endocrine conditions:
 - Type 1 diabetes mellitus
 - AI thyroiditis including Hashimoto's disease, Graves' /Basedows' disease
- Inflammatory bowel / hepatic diseases:
 - Crohn's diseases
 - Ulcerative colitis
 - Autoimmune hepatitis

9.3.2. Secondary endpoints

Secondary endpoint is the occurrence of new onset of individual confirmed autoimmune disease during the following specific periods:

- Occurrence of Guillain Barré syndrome (including Miller Fisher syndrome and other variants), and autoimmune haemolytic anaemia within two months following the administration of the first dose of Cervarix;
- Occurrence of idiopathic thrombocytopenic purpura (ITP) within six months following the administration of the first dose of Cervarix;
- Occurrence of multiple sclerosis, transverse myelitis, optic neuritis, other demyelinating diseases (see the two sub-bullets for these diseases in Section 9.3.1), auto-immune uveitis, systemic lupus erythematous (SLE), rheumatoid arthritis (RA), juvenile rheumatoid arthritis (JRA), Still's disease, psoriatic arthritis, ankylosing spondylitis, type 1 diabetes mellitus, auto-immune thyroiditis (including Hashimoto's disease, Graves'/Basedows' disease), and inflammatory bowel / hepatic disease (Crohn's disease, ulcerative colitis and autoimmune hepatitis) within one year following the administration of the first dose of Cervarix.

9.3.3. Data to be collected

9.3.3.1. Subjects characteristics

The following data will be extracted for the analysis population:

• Demographic characteristics: birth month and birth year, sex, region, practice region identifier, date of death (if applicable) and acceptable patient flag

- CPRD GOLD information: CPRD GOLD start date, first registration date, current registration date, registration gaps, registration status, transfer-out date, transfer-out reason
- HES information: Linkage to HES data
- Vaccines:

Administration of any other vaccine from one year before the reference date and until the end of follow-up will be collected: date of vaccination, medcodes and immunization type will be extracted from the immunisation file. Cross-tabulation of medcodes and vaccine names/class is detailed in Annex 5.

• Health care resource utilization: number of primary care resource utilization during the year before the reference date.

9.3.3.2. Clinical outcomes

Occurrence of auto-immune diseases defined as study endpoints will be identified using defined algorithms (see Annex 5).

For each case, the following data will be extracted:

- Medcode(s)
- Date of event

The associated "free text" (event text ID) if any will be identified. For all the identified cases of auto-immune diseases, the associated free text will be reviewed by a GSK-identified reviewer for confirmation and determination of the date of first symptoms of NOAD.

9.3.3.3. Other derived variables

The following variables will be derived from the CPRD GOLD data:

- Subject's date of birth will be defined as the 15th of the birth month and birth year. If the birth month is missing, the birth date will be defined as the 30th June of the birth year
- Incomplete dates (except for vaccination date which is the reference date) will be substituted as follows for calculation of age and/or time to event; if the day is missing the date will be defined as the 15th of the month, if both the day and the month are missing, the date will be defined as 30th June of the year
- Age at a specific event will be computed as the difference between the date of the event and the date of birth

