9.7.5. Analysis of co-primary endpoints

9.7.5.1. Cohort analysis

The primary analysis will compare the incidence rates of the primary outcomes of interest between the Cervarix exposed female cohort and the historical unexposed female cohort. Results will be presented as the incidence rate ratio and the incidence difference. Exposed person-time will be defined as the period between the reference date and the earliest of the following events:

- End of study period (defined as 12 months after the reference date);
- Date of de-enrolment from CPRD GOLD;
- Date of unspecified HPV vaccine or Gardasil or Cervarix for unexposed cohort;
- Date of first diagnosis of the outcome of interest.

Incidence rates for auto-immune diseases will be calculated by dividing the number of cases by person-time. A Poisson regression model will estimate the risk ratio and its 95% confidence interval. The Poisson model will include the number of cases in each cohort as the dependent variable, the exposure status as a binary independent variable, the age-group ([9-18],[18-25]) as a covariate, and the log-transformed total person-year as an offset.

Sensitivity analyses

Sensitivity analyses will be performed:

- Incidence rates for NOAD in the exposed cohort will be calculated after each dose by dividing the number of cases by the total person-time. Exposed person-time will be defined as the period between the date of the dose administration and the earliest of the following events:
 - End of risk period (defined as 6 months after each dose);
 - Date of the next Cervarix dose;
 - Date of de-enrolment from CPRD GOLD;

- Date of unspecified HPV vaccine or Gardasil;
- Date of first diagnosis of the outcome of interest.
- Separate analysis will be performed for subjects younger/older than 18 years.
- Analysis including possible confounding factors (if available): other vaccination, age, region, healthcare resource utilization, categorization will be determined based on the available data.
- In case of more than 5% of NOAD with unknown/incomplete date, a sensitivity analysis will be done including these events as occurring during the risk period. This imputation will be done for the four cohorts.
- The same comparison will be done between the two male cohorts. In case of significant difference between these two male cohorts, the primary analysis will be adjusted for time effect other than Cervarix (see Section 9.7.5.1 for the detailed statistical models).

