9.7.8.1. Handling of missing data

Missing data will not be substituted.

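### The rule for incomplete onset dates ignores the known reference date, and section 9.7.8.1 conflicts with it on its face

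*Protocol*

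**What the plan says.** Three parts of the protocol bear on a partial onset date.

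- Section 9.3.3.3 sets the rule and its scope: "Incomplete dates (except for vaccination date which is the reference date) will be substituted as follows for calculation of age and/or time to event". A date that lacks only its day goes to the 15th. For a date known only by its year the rule is: "if both the day and the month are missing, the date will be defined as 30th June of the year". The reference date plays no part in the rule.
- Section 9.7.8.1, on missing data, reads in full: "Missing data will not be substituted". It makes no exception for dates.
- Section 9.7.5.1 adds a conditional check: "In case of more than 5% of NOAD with unknown/incomplete date", then "a sensitivity analysis will be done including these events as occurring during the risk period", in all four cohorts.

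Section 9.4.2 has a contract research organisation, and where needed a blinded expert panel, decide whether onset falls within one year after the reference date. The protocol does not say whether that decision or the substituted date prevails.

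**The concern.** The endpoints are defined by windows that start at the first dose: 12 months for the co-primary composites (9.3.1), 2 months for Guillain-Barré syndrome and autoimmune haemolytic anaemia, and 6 months for idiopathic thrombocytopenic purpura (9.3.2). A fixed calendar date can fall before the dose even when the true onset followed it. A girl vaccinated on 1 October 2008 whose onset was in November, but is recorded only as 2008, is dated 30 June 2008.

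Partial dates are plausible here. Onset means first symptoms, determined partly from free text (9.3.3.2), and 9.4.2 and 9.9 both name onset timing as a weakness of the data. An analyst who follows 9.3.3.3 and one who follows 9.7.8.1 could classify the same case differently. At stake are dilution of a real effect on the co-primary endpoints and the counts for the short-window endpoints.

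**Working it through.** The protocol gives no figure for partial dates, so there is none to reproduce. The check is a calendar count. For each reference date, take every onset day in the window (the dose day counts as day 1), apply 9.3.3.3, and see where the substituted date falls.

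Assumptions: a constant daily onset rate, and windows of 365, 183 and 61 days. Two patterns of reference date are used. One is uniform over the year. The other is 1 September to 30 November, which is an assumption: 9.2.1 gives school delivery and academic years but no distribution by month.

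**1. Year-only dates, 12-month window, September to November doses.** Let r be the days from the dose to 31 December inclusive. Those onset days all become 30 June, before the dose.
- 1 September: 122/365 = 33.4%. 1 October: 92/365 = 25.2%. 1 November: 61/365 = 16.7%.
- Mean r = (122 + 32)/2 = 77, so 77/365 = 21.1% move out.
- Onsets in the next calendar year become 30 June of that year, inside the window. This includes those between the window's end and 31 December, again 77 days on average. So 21.1% also move in.

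**2. Year-only dates, 12-month window, uniform reference dates.**
- Dates after 30 June: (184/365) × (92.5/365) = 12.8% move before the reference date.
- Dates up to 30 June: (181/365) × (90/365) = 12.2% move past the window.
- Equal shares move in, so the net count is unchanged when there is no effect.

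**3. Year-only dates, short windows, September to November doses.**
- 2 months: the 62 doses dated 1 September to 1 November have all 61 onset days in the dose year. The 29 doses dated 2 to 30 November have 46 on average. (62 × 61 + 29 × 46)/(91 × 61) = 5,116/5,551 = 92.2% move before the dose. The other 7.8% move past the window.
- 6 months: 77/183 = 42.1% move before and 57.9% past.
- 30 June is never inside either window, so no year-only onset stays and none moves in.

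**4. Day-missing dates, September to November doses.** An onset is dated before the dose only when the dose falls after the 15th and onset is later in the same month (dose 20 September, onset 25 September, substituted 15 September). Mean days affected: (120 + 136 + 120)/91 = 4.13. That is 1.1% of a 12-month window, 2.3% of 6 months and 6.8% of 2 months.

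**5. Effect on a co-primary risk ratio of 2.** Let p be the share of cases with year-only dates, which the protocol does not give. The comparator count is taken as unchanged, because gains and losses balance at no effect.
- Excess spread over the year, autumn doses: (0.789 × 2 + 0.211 × 1)/2 = 0.895 of year-only cases are counted. Uniform dates: (0.750 × 2 + 0.250 × 1)/2 = 0.875.
- All excess in the first 61 days, autumn doses: 7.8% of the year-only excess is kept.

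| Scenario | Formula | p = 5% | p = 20% |
|---|---|---|---|
| Spread, autumn | 2 × [(1 − p) + 0.895p] | 1.99 | 1.96 |
| Spread, uniform | 2 × [(1 − p) + 0.875p] | 1.99 | 1.95 |
| Early, autumn | 2(1 − p) + 1.078p | 1.95 | 1.82 |

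**6. The trigger.** If the 5% is taken of the roughly 280 cases for review in 9.9, then 0.05 × 280 = 14 incomplete dates could occur without the check being run.

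**7. Size of a 2-month endpoint.** Table 1 gives female Guillain-Barré rates of 0.4 to 2 per 100,000 per year at ages 18 to 25. 65,000 × 61/365 = 10,863 person-years, hence 0.04 to 0.22 expected cases.

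**The case against.** The best defence is that 9.3.3.3 may rarely decide anything. The review in 9.4.2 uses codes, laboratory and treatment files, free text and hospital data to judge whether onset is in the window. Section 9.2.5.1 excludes anyone with an autoimmune code in the year before the reference date, so an included case's first code will normally follow it. This stands as a limit on how often the rule bites. It does not remove the gap, because the protocol never says that the review overrides the substituted date, and a review cannot supply a day or month that the record lacks.

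Section 9.7.8.1 can be read as covering only wholly missing values. That is possible, but the section does not say so. Section 9.7.5.1 is a sensitivity analysis and is meant to differ from the main rule, so a reader who counts three rival rules goes too far. The conflict is between 9.3.3.3 and 9.7.8.1.

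A reader might also infer that the rule drops post-vaccination cases and so masks harm. The documents do not support that. For the co-primary endpoints, cases move in as well as out, and the net effect at no association is nil. The 92% figure needs year-only dates, a 2-month window and autumn doses together. The endpoints with that window are descriptive, modelled only with more than 10 cases and not confirmatory (9.7.6), and fewer than one Guillain-Barré case is expected.

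**Conclusion.** The point holds as a defect in a rule that the protocol itself fixes. It substitutes dates without regard to the reference date, another section conflicts with it, and its place relative to the case review is not stated. For the co-primary endpoints the consequence is misplacement in both directions and some dilution. For the 2- and 6-month endpoints, year-only onsets after an autumn dose are lost altogether. The day-missing rule matters little.

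The effect on the co-primary risk ratio is probably small, and it scales with the unknown share of partial dates. The autumn figures rest on an assumed dose calendar; the uniform figures do not. The repair is worth making before analysis because it is cheap and removes a choice that could otherwise be made with the data in view.

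**What to change.** - In 9.3.3.3, state that the onset classification from the contract research organisation or panel takes precedence, and that any date rule applies only to dates still partial after that review.
- Classify a remaining partial onset by its possible date range when that range lies wholly inside or wholly outside the window.
- When the range spans a window boundary, run the analysis once with the event inside the window and once with it outside. Do this for each window and all four cohorts, and remove the 5% trigger in 9.7.5.1.
- In 9.7.8.1, limit the statement to values other than partial dates.

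The cost is some wording and one more sensitivity analysis. The inclusive run will count some onsets that truly fell outside the window. It may do so unequally between cohorts if their reference dates are spread differently over the calendar year. That is possible because 9.2.2 draws historical dates at random over two years, whereas 9.1.2 takes them from the exposed dates minus three years.
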